- A. Pre-infusion Period 2 (will last six days prior to infusion): 1) Questionnaires: Subjects will be asked to complete painevaluation questionnaires (BPI, NRS, and McGill). Anxiety evaluation will be completed by patients using HAD and STAltrait and state parts questionnaires. 2) Participants will be asked to wear the ACTIHEART device during 3 days prior to the infusion, during the 3 infusion days, and in the three days after the infusion.
- B. Infusion period 2 (oxytocin Infusion over three days): Participants will arrive for three consecutive day visits. 1) Subject will be instructed to eat a light, non-fatty breakfast. 2) Vital signs (blood pressure and heart rate), including weight and height will be collected prior to infusion. 3) Provide two questionnaires (BPI, NRS) for subjects to complete. 4) Nursing staff will establish IV access for infusion and blood collection. 5) Prior to infusion, blood samples will be obtained for oxytocin levels and for storage. 6) Oxytocin infusion (200ml, 0.9% NaCl with 1 IU of oxytocin, over 40 minutes*). Blood pressure and heart rate will be monitored during and after the infusion. 7) Blood sample (for oxytocin levels and storage) will be collected immediately after the infusion on day 1. Note: This will require a second vein access to be set prior to the infusion (this sample cannot be collected from the place of the OXT / Placebo infusion). 8) Administer both the NPI and STAI-state part questionnaires prior to subject's discharge. Subjects will be discharged 2 hours after the infusion.

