Provide a description of your plan for data analysis. State the types of comparisons you plan (e.g. comparison of means, comparison of proportions, regressions, analysis of variance). Which is the PRIMARY comparison/analysis? How will the analyses proposed relate to the primary purposes of your study?

The primary goal of this study is to compare the change in pain scores between the pre and post placebo treatment period vs pre and post IV oxytocin treatment period.

Changes from baseline to endpoint will be evaluated by paired T test

Baseline and endpoint that will be compared:

- 1) Maximum pain level, minimum pain level, average pain, and pain-effect scores (using the BPI) in the days prior to each infusion period (placebo and oxytocin) and maximum pain level, minimum pain level, average pain and pain-effect scores (using the BPI) in the days prior to each infusion period (placebo and oxytocin) and average pain and pain-effect scores in the days after each infusion period.
- 2) Comparing the difference in maximum pain level, minimum pain level, average pain and pain-effect scores (using the BPI) pre and post infusion between placebo and oxytocin treatment.
- 3) Simple pain scale scores (NPRS) prior to infusion and simple pain scale scores 2 hours after the infusion on every day of infusion in both infusion periods (placebo and oxytocin).
- 4) Anxiety and depression scores prior and post infusion periods and comparing scores following placebo and oxytocin treatments
- 5) Changes in heart rate, inter-beat-interval (IBI), and physical activity as measured by ACTIHEART comparing data collected prior, during and after placebo and oxytocin treatments.

In addition we will compare heart rate, blood pressure with oxytocin infusion compared to levels with placebo. We will compare oxytocin levels in the plasma prior to the first infusion, immediately after the first infusion and 2 hours after the first infusion for both placebo and oxytocin.

P-values of 0.05 or less will be considered statistically significant

Section H: Potential Risks/Discomforts

H1. Potential Risks/Discomforts

Describe and assess any potential risks/discomforts; (physical, psychological, social, legal, or other) and assess the likelihood and seriousness of such risks:

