The risks associated with venipuncture are minimal. Adverse events for using IV oxytocin as reported in the literature (based on the use of this drug in pregnant or postpartum women in dose that is at least 10 folds higher than the one used in this study) are as follows:

Common effects - Nausea, Vomiting, loss of appetite, stomach pain Runny nose, sinus pain Memory problems

Rare effects- Anaphylactic reaction Premature ventricular contractions Cardiac arrhythmia Hypertensive episodes

Afibrinogenemia Subarachnoid hemorrhage Intrinsic antidiuretic effect (risk for water intoxication) Postpartum hemorrhage Pelvic hematoma Rupture of uterus (during labor)

In this study we suggest giving a slow infusion of 1 unit of IV oxytocin over 40 minutes. This dose is lower than the dose used in clinical practice and the rate of infusion is slower than the rate that was reported to cause adverse effects in females treated with IV oxytocin to induce labor (Thomas, Koh, and Cooper, 2007 PMID 17142825). Given these data, we estimate that the risk for adverse effects in our study will be very low. Louvel et al (1996, PMID 9014776) published a study that measured the effect of IV oxytocin on threshold of pain caused by colonic distention in males and non-pregnant females with irritable bowel syndrome. In this study subjects were infused with continuous drip of 10, 20, 30 or 50 mU/min oxytocin for 60-70 minutes. In this study four patients receiving oxytocin at a rate of 50mU/min had headache during the infusion and could not continue with the study. No adverse effects had been reported in the other treatment groups that received 10, 20, and 30 mU/min infusion. In our study, the infusion rate will be 1 unit in 40 minutes (25mU/min).

Hypermobile EDS is more prevalent in females and the symptoms are usually more severe in females and more females come to medical attention. Oxytocin secretion in the body is dynamic and can be affected by multiple factors including the menstrual period. In order to have minimum variation between tested individuals we chose to conduct this study in females, all participants will be at the same stage of their menstrual cycles. We are not aware of any difference in the risk from using oxytocin in females vs males.

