The Actiheart device is supplied by the CNRC team to the research team. The device will be provided to and collected from the participant via FedEx service or will be handed to the patient at one of the research visits (example: screening visit). After the completion of data collection by the participant, the research team will physically hand the device to the CNRC team for further data analysis. Each device will have a patient number that was coded by the research team. CNRC team will have no participant's identifying data on the device. CNRC team will receive subject's gender, height, weight, and date of birth to help in data analysis. For data analysis, CNRC staff has controlled access to the Actiheart device database which is maintained on BCM IT server. Also, the data collected is not shared with device manufacturer or any other third party.

Please note: The CNRC staff has provided the Actiheart device information and will provide statistical analysis for the study.

Where applicable, all research data will be coded and transmitted via secure e-mail accordingly.

Will you obtain a Certificate of Confidentiality (COC) for this study?

No

Please further discuss any potential confidentiality issues related to this study.

N/A

Section L: Cost/Payment

Delineate clinical procedures from research procedures. Will subject's insurance (or subject) be responsible for research related costs? If so state for which items subject's insurance (or subject) will be responsible (surgery, device, drugs, etc). If appropriate, discuss the availability of financial counseling.

Research-related procedures are incurred by the study. There are no standard of care procedures for this study. Oxytocin will be covered by the study.

If subjects will be paid (money, gift certificates, coupons, etc.) to participate in this research project, please note the total dollar amount (or dollar value amount) and distribution plan (one payment, pro-rated payment, paid upon completion, etc) of the payment.

Dollar Amount:

400

Distribution Plan:

Each completed treatment period will involve \$200 in compensation for a total at \$400 for study participation. Additionally, reimbursement for applicable travel-related expenses (parking, mileage, ground transport, hotel and flights) will be covered ranging up to but not limited to \$600 for study participation. Study compensation and reimbursement will be provided through Baylor's ClinCard program.

Section M: Genetics

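### G2 compares infusion blood pressure and heart rate only as levels by treatment; adding per-participant peak changes and counts would show the isolated episodes that H1 lists

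*Combined protocol and SAP*

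**What the plan says.** H1 gives the harms reported for IV oxytocin, drawn from obstetric use at doses at least ten times higher than here. Among them are "Rare effects- Anaphylactic reaction Premature ventricular contractions Cardiac arrhythmia Hypertensive episodes" and "Intrinsic antidiuretic effect (risk for water intoxication". H1 expects the risk in this study to be very low.

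F2 schedules the relevant measurements in both infusion periods. Before infusion: "Vital signs (blood pressure and heart rate), including weight and height will be collected prior to infusion". Then: "Blood pressure and heart rate will be monitored during and after the infusion". Participants leave 2 hours after the infusion. The supplied text does not say how often readings are taken.

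G2 opens its list of comparisons with "Changes from baseline to endpoint will be evaluated by paired T test". After the five listed items it adds "In addition we will compare heart rate, blood pressure with oxytocin infusion compared to levels with placebo", and it closes with "P-values of 0.05 or less will be considered statistically significant". Nothing in G2 refers to a peak value, a limit, a number of participants affected or weight. The one stated use of weight is in Section K: "CNRC team will receive subject's gender, height, weight, and date of birth to help in data analysis".

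H2 classes the study as greater than minimal risk and refers to a Data and Safety Monitoring Plan attached in Section S. F2 places the Schedule of Assessments there too. Neither attachment is in the supplied document.

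**The concern.** A hypertensive episode happens to one person over a short time. A comparison of levels between treatments answers a different question: whether the group as a whole runs higher or lower on oxytocin. If levels means averages, a marked rise in one or two participants is spread over everyone, and it also inflates the standard deviation against which the average is judged. The result would most likely read as no significant difference, although the readings that show the episode had been collected.

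What is at stake is how the pilot's vital-sign results can be read. H1 predicts very low risk, and Section I says clinical uptake could be fast because the drug is already approved. A non-significant level comparison could be taken as support for that prediction, yet such a comparison has little ability to contradict it.

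**Working it through.** **Inputs from the plan.** G1: 17 evaluable pairs, 20 enrolled, two-sided alpha 0.05, power 0.8, dz = 0.73. G2: paired t test, significance at p ≤ 0.05.

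**The plan's own figure.** Exact paired t test power at dz = 0.73 is 77.9% for n = 16 and 80.7% for n = 17, so 17 is the smallest n reaching 80%. With 15% dropout, 17/0.85 = 20. Both figures reproduce, and n = 17 is used below.

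**Step 1: a result that does not depend on the size of the rise.** Suppose k of n participants have the same rise D on oxytocin and every other oxytocin-minus-placebo difference is 0.

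- Mean difference = kD/n.
- Variance of the differences = D²·k(n−k)/[n(n−1)].
- t = mean/(SD/√n) = √[k(n−1)/(n−k)]. D cancels.

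For n = 17 (16 degrees of freedom, critical value 2.12):

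| k | t | p |
|---|---|---|
| 1 | √(16/16) = 1.00 | 0.33 |
| 2 | √(32/15) = 1.46 | 0.16 |
| 3 | √(48/14) = 1.85 | 0.083 |
| 4 | √(64/13) = 2.22 | 0.041 |

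Significance first appears at four affected participants. With n = 20 it is also four (p = 0.042).

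**Step 2: with ordinary variability.** The documents give neither the size of a rise nor the spread of paired differences, so these are assumptions: D from 30 to 60 mmHg and SD of the paired differences from 8 to 12 mmHg. At 40 mmHg the mean shifts by 40k/17 = 2.4, 4.7 and 7.1 mmHg for k = 1, 2, 3. Simulated trials with n = 17 gave p ≤ 0.05 in these proportions:

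| k | Rise fully reflected in the analysed value | Three days averaged, rise on one day |
|---|---|---|
| 1 | 1–5% | about 5% |
| 2 | 4–9% | 6–8% |
| 3 | 15–19% | 7–15% |

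For one participant, the test rejects no more often than its 5% false-positive rate. Even for three, at least about 81% of trials would be non-significant.

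**Step 3: what a count would report.** Exact (Clopper-Pearson) 95% intervals for n = 17:

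- 1/17 = 5.9% (0.1% to 28.7%)
- 2/17 = 11.8% (1.5% to 36.4%)
- 3/17 = 17.6% (3.8% to 43.4%)
- 0/17: one-sided 95% upper limit 1 − 0.05^(1/17) = 16.2%

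**The case against.** **G2 does not say means or t test for vital signs.** This is correct. The paired t test sentence introduces the five numbered items; the blood pressure sentence follows them and names no test or summary. Nor does G2 call it a safety analysis. Dilution is therefore conditional: it follows if the only named test is applied to averages.

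**Individual harms may be handled elsewhere.** A reader might infer that episodes or fluid retention would go unreported, or that pre-infusion weight is the only fluid measure collected. The documents do not support either inference. The monitoring plan and the Schedule of Assessments are in Section S, which is not available here.

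**The episodes may not occur.** H1 calls them rare and takes them from much higher doses, whereas one to three of 17 is 6% to 18%. This also stands. However, zero or one event is exactly when a count with an exact interval is more informative than a mean.

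**A count is not a more powerful test.** True: three participants affected on oxytocin and none on placebo gives an exact McNemar p of 0.25. The gain is that the episode is visible and its uncertainty stated, not that it becomes significant.

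**Weight and Actiheart.** It is tempting to ask for counts of irregular inter-beat intervals, since H1 lists arrhythmia. The documents do not show that the device output supports such counts, F2 lets the study proceed if wear is incomplete, and Section D defines the Actiheart outcome as a functional consequence of pain. A comparison of mean weight change would repeat the averaging problem. Weighing at every visit is implied by the three-visit layout in F2 but not stated.

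**No text says non-significance will be presented as safety.** This is correct. The very-low-risk statement is a prior expectation based on dose and literature. The misreading is a possibility to guard against, not a stated intention.

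**Conclusion.** The point holds in a limited form. G2 analyses infusion blood pressure and heart rate only as a comparison of levels, and it does not specify the summary. Under the natural reading (means and the paired t test), a rise in one to three of 17 participants would usually be non-significant. The first calculation needs no assumption about the size of the rise, only that the other differences are zero. The simulated percentages rest on assumed rises of 30 to 60 mmHg and SDs of 8 to 12 mmHg.

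The stronger reading, that the trial would miss or fail to report adverse events, is not supported: monitoring is scheduled, and the safety plan lies in an attachment not supplied. Severity is minor. It is worth doing because a better summary is available from readings already planned.

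**What to change.** Keep the level comparison in G2 and add:

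> For each participant and infusion day, the largest rise and fall in systolic and diastolic pressure and heart rate from that day's pre-infusion value through discharge will be derived and listed. The number and proportion of participants exceeding limits fixed by the investigator before the first participant's first infusion will be reported by treatment with exact 95% confidence intervals. Absence of a significant mean difference will not be reported as evidence of safety.

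The limits are for the investigator to choose. They should be fixed before any infusion because only participants are blinded, so staff will see the placebo readings first.

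If weight is recorded at each infusion visit, list each participant's day-1 to day-3 change by period. Note that, being taken before infusion, it reflects only the first two infusions.

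The cost is a few sentences in G2 and a few descriptive tables, with no new visit, test or participant. The largest change depends on how often readings are taken, so reading times should match between periods. The downside is wide intervals and a less favourable safety statement, as with the 16% upper limit after zero events in 17.

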- A. Pre-infusion Period 1 (will last six days prior to infusion): 1) Questionnaires: Subjects will be asked to complete painevaluation questionnaires (BPI, NRS, and McGill). Anxiety evaluation will be completed by patients using HAD and STAltrait and state parts questionnaires. 2) Participants will be asked to wear the ACTIHEART device during 3 days prior to the infusion, during the 3 infusion days, and in the three days after the infusion. The instructions for the Actiheart monitor and activity record including patient visit reminders will be provided to subjects.
- B. Infusion period 1 (Placebo Infusion over three days): Participants will arrive for three consecutive day visits. 1) Subject will be instructed to eat a light, non-fatty breakfast. 2) Vital signs (blood pressure and heart rate), including weight and height will be collected prior to infusion. 3) Provide two questionnaires (BPI, NRS) for subjects to complete. 4) Nursing staff will establish IV access for infusion and blood collection. 5) Prior to infusion, blood samples will be obtained for oxytocin levels and for storage. 6) Placebo infusion (200ml, 0.9% NaCl, over 40 minutes). Blood pressure and heart rate will be monitored during and after the infusion. 7) Blood sample (for oxytocin levels and storage) will be collected immediately after the infusion on day 1. Note: This will require a second vein access to be set prior to the infusion (this sample can not be collected from the place of the OXT / Placebo infusion). 8) Administer both the NPI and STAI-state part questionnaires prior to subject's discharge. Subjects will be discharged 2 hours after the infusion.
- C. Post Infusion Period 1 Pain & Anxiety Evaluation for 6 days: Participants will complete questionnaires over six days at the investigator's discretion: BPI, NRS, McGill on days 1, 3, and 5 after infusion and HAD and STAI-state and trait questionnaires on day 6 after infusion.

Treatment period 2 will start at least 2 weeks after the completion of treatment period 1 and 7-12 days after the first day of menstruation for subjects. Treatment period 2 will consist of the following:

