According to accepted guidelines, the maximum amount of blood to be drawn over a 24-hour period is 3% of total blood volume if the subject is an outpatient, and 5% of total blood volume if the subject is an inpatient. The maximum amount of blood which can be safely drawn from research participants in any one-month period should not exceed 10% of the total blood volume.

All the participants in this study are adults. On average an adult have blood volume of approximately 5 litres. This will allow us to draw maximum of 150 ml per 24 hours and 500 ml over a total period of one month. The amount of blood planned to be drawn will be lower than the maximum allowed. A record of total blood volume withdrawn during each visit will be maintained in the subject's medical record.

Blood drawn during each treatment period (in one month) include: Day 1: Oxytocin levels (10ml) and storage blood (10ml) at preinfusion, immediately post infusion, and 2 hours post infusion. This sums up to 60 ml per 24 hours. Day 3: Storage blood (10ml) at preinfusion and 2 hours post infusion. This sums up to 20 ml per 24 hours. Total of 80ml per one month.

The risk of blood draw may include bruising, pain and infection at the place where the needle was inserted.

For the EKG test, you may develop a mild rash or skin irritation where the electrodes were attached. If any paste or gel was used to attach the electrodes, you may have an allergic reaction to it. This irritation usually goes away once the patches are removed, without needing treatment.

For the ACTIHEART device - mild skin irritation where the electrodes are attached. We recommend that participants will alternate the place of electrodes every day between two suggested sites.

A risk of loss of confidentiality may be possible but every effort by research staff will be made to reduce or eliminate any risk for the subjects.

H2. Data and safety monitoring plan

Do the study activities impart greater than minimal risk to subjects? Yes

NOTE: The answer to the questions in H2 requires the completion of the form: 'Section H â€" Data and Safety Monitoring Plan' as an attachment in Section S.

H3. Coordination of information among sites for multi-site research

Is the BCM Principal Investigator acting as the SPONSOR-INVESTIGATOR for this multi-site research? No or Not Applicable

Is BCM the COORDINATING CENTER for this multi-site research?

No or Not Applicable

Section I: Potential Benefits

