How would you classify your genetic study?

Discuss the potential for psychological, social, and/or physical harm subsequent to participation in this research. Please discuss, considering the following areas: risks to privacy, confidentiality, insurability, employability, immigration status, paternity status, educational opportunities, or social stigma.

n/a

Will subjects be offered any type of genetic education or counseling, and if so, who will provide the education or counseling and under what conditions will it be provided? If there is the possibility that a family's pedigree will be presented or published, please describe how you will protect family member's confidentiality?

n/a

Section N: Sample Collection

SAMPLE: Blood

What is the purpose of the sample collection?

Blood will be collected for the measurement of oxytocin levels. Blood will be also collected for storage for later confirmation of research findings.

For blood draws, specify the amount drawn, in teaspoons, at each visit and across the course of the subjects entire participation time.

All participants are adults. Blood will be collected on day 1 only. The two treatment periods are at least one month apart. On each treatment period, blood will be drawn prior to treatment and immediately after treatment.

Visit 1 in treatment period 1 - blood draw will include in each visit: Day 1 - Pre-treatment: 10 ml (2 teaspoons) for oxytocin measurements, 20 ml (4 teaspoons) for storage. immediately after treatment: 10 ml (2 teaspoons) for oxytocin measurements, 20 ml (4 teaspoons) for storage. Total of 60 ml of blood for this day (12 teaspoons).

Total blood collection during treatment period 1 - 60 ml (12 teaspoons)

Visit 1 in treatment period 2 - blood draw will include in each visit: Day 1 - Pre-treatment: 10 ml (2 teaspoons) for oxytocin measurements, 20 ml (4 teaspoons) for storage. immediately after treatment: 10 ml (2 teaspoons) for oxytocin measurements, 20 ml (4 teaspoons) for storage. Total of 60 ml of blood for this day (12 teaspoons).

Total blood collection during treatment period 1 - 60 ml (12 teaspoons)

Samples for oxytocin measurements will be obtained on ice and plasma will be stored immediately.

Is there the possibility that cell lines will be developed with this sample?No

Sample will be obtained from:

Other: Research subject

Will the sample be stripped of identifiers?

Νc

If sample will be released outside the hospital:

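### The 2-hour oxytocin sample that G2 compares and H1 counts is missing from F2 and Section N; H1 and N also disagree on draw days, storage volume and period total

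*Combined protocol and SAP*

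**What the plan says.** **G2 (Data Analysis).** After its five numbered comparisons, the section adds a comparison of "oxytocin levels in the plasma prior to the first infusion, immediately after the first infusion and 2 hours after the first infusion", to be made for both treatments.

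**H1 (Potential Risks/Discomforts).** The blood budget agrees with G2 on the time points: "Day 1: Oxytocin levels (10ml) and storage blood (10ml) at preinfusion, immediately post infusion, and 2 hours post infusion". It then adds a second draw day: "Day 3: Storage blood (10ml) at preinfusion and 2 hours post infusion". It closes with "Total of 80ml per one month".

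**F2 (Procedure), item B of each treatment period.** Step 5 reads "Prior to infusion, blood samples will be obtained for oxytocin levels and for storage", with no day stated, under a heading that covers three daily visits. Step 7 reads "Blood sample (for oxytocin levels and storage) will be collected immediately after the infusion on day 1". Step 8 lists only questionnaires before the participant leaves, and then "Subjects will be discharged 2 hours after the infusion". No 2-hour blood draw appears in either period.

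**Section N (Sample Collection).** Collection is restricted to day 1, and "On each treatment period, blood will be drawn prior to treatment and immediately after treatment". Each of the two draws is itemised as 10 ml for oxytocin and 20 ml for storage, giving 60 ml per period.

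**The concern.** G2 states a comparison at three time points, but the two sections that describe what is collected supply only two. A plasma sample that is not drawn on the day cannot be recovered later, so a site working from F2 or N would find at analysis that the 2-hour comparison cannot be made in either period.

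The second problem is separate. H1 and N describe the same blood collection with different draw days, storage volumes and period totals, so the volumes in the risk section are not those in the sampling section.

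**Working it through.** **Time points, side by side (day-1 oxytocin samples, per period)**

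| Section | Pre-infusion | Immediately after | 2 hours after |
|---|---|---|---|
| G2 | yes | yes | yes |
| H1 | yes | yes | yes |
| F2 | yes | yes | not listed |
| N | yes | yes | not listed |

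F1 says only that blood is taken before and after the infusion, which does not settle the matter.

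**Samples lost if F2 or N is followed**

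- Per participant: 2 instead of 3 per period, so 2 × 2 = 4 instead of 2 × 3 = 6 over the study.
- For the 20 to be enrolled (G1): 20 × 2 periods = 40 undrawn 2-hour samples.
- For the 17 on whom G1 bases its power: 17 × 2 = 34.

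**Volumes.** Formula: time points × (oxytocin ml + storage ml), summed over draw days. Each section's own total reproduces.

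- H1, day 1: 3 × (10 + 10) = 60 ml, of which 30 ml is for oxytocin and 30 ml for storage.
- H1, day 3: 2 × 10 = 20 ml, all storage.
- H1, period: 60 + 20 = 80 ml, as stated. Two periods: 160 ml.
- N, day 1: 2 × (10 + 20) = 60 ml, of which 20 ml is for oxytocin and 40 ml for storage.
- N, period: 60 ml, as stated. Two periods: 120 ml.

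The difference per period is 80 − 60 = 20 ml, which equals H1's day-3 storage blood. The day-1 totals agree at 60 ml only by coincidence (3 × 20 against 2 × 30), so a check of day-1 totals alone would miss the conflict.

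**F2 step 5.** Read literally, it calls for pre-infusion oxytocin and storage blood at all three visits, which fits neither H1 nor N. Under that reading:

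- At H1's volumes, day 2 gains 10 + 10 = 20 ml and day 3 gains 10 ml for oxytocin: 80 + 20 + 10 = 110 ml per period.
- At N's volumes without a 2-hour sample, days 2 and 3 each gain 10 + 20 = 30 ml: 60 + 30 + 30 = 120 ml per period.

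**Against the limits.** H1 assumes a blood volume of 5 litres: 3% gives 150 ml per 24 hours and 10% gives 500 ml per month. Both stated schedules take 60 ml on their heaviest day. Even if both periods fell within one month, H1's 160 ml would be below 500 ml.

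**The case against.** The strongest reply is that what staff actually draw may be governed by the Schedule of Assessments. F2 places it in Section S and says it goes to study staff; it was not among the documents available. F2 step 7 requires an immediate post-infusion sample but does not exclude others. The 2-hour draw may therefore be taken in practice, and the count of 40 lost samples is conditional. That stands: the conflict in the text is certain, while the loss of data is a risk. The Schedule could show which version is used, but it cannot make F2, G2, H1 and N agree. Section N is also explicit, since its itemised total leaves no room for a 2-hour tube.

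A second reply is that the stakes are low. Section D does not list oxytocin level as an outcome, and G2 introduces it as an addition. The volume differences concern mainly storage blood, which no G2 comparison uses, and H1 requires the volume drawn at each visit to be recorded. This too is correct and limits the weight of the point. It does not remove the fact that one stated comparison may have no data.

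**Conclusion.** The concern holds. G2 and H1 include a 2-hour day-1 oxytocin sample that F2 and N do not list. If staff follow F2 or N, one of the three time points in G2's comparison is empty in both periods (40 samples for 20 participants, 34 for 17). Separately, H1 and N disagree on draw days (1 and 3 against 1 alone), storage per time point (10 against 20 ml) and period total (80 against 60 ml).

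The pre-infusion and immediate post-infusion oxytocin comparisons, the pain comparison, the sample size and the power are unaffected, and no stated blood limit is approached. The text conflict rests on no assumption. The data loss assumes that the Schedule of Assessments does not direct staff otherwise, and the counts assume that the stated number of participants complete both periods. The correction should be made, because it is cheap and a missed sample cannot be replaced.

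**What to change.** Adopt one sampling schedule and state it identically in F2, G2, H1, N and the Schedule of Assessments. For the 2-hour sample, either:

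- add it to F2 step 7 in both periods and to N; or
- delete the 2-hour comparison from G2 and the 2-hour day-1 draw from H1.

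In either case, also state whether H1's day-3 storage draws stay, whether F2 step 5 applies to day 1 only or to every infusion day, and whether storage is 10 or 20 ml per time point. Then restate the period total. With pre-infusion oxytocin on day 1 only, the totals are:

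| | H1 volumes | N volumes (plus any day-3 blood) |
|---|---|---|
| With 2-hour sample | 80 ml (60 without day 3) | 60 + 10 = 70 ml (oxytocin only at 2 hours) or 60 + 30 = 90 ml (with storage) |
| Without 2-hour sample | 2 × 20 + 20 = 60 ml (40 without day 3) | 60 ml |

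The largest single day among these is 90 ml, below 150 ml. If step 5 is meant to apply daily, the extra draws must be added.

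The cost is text alignment across the four sections and a check of the Schedule. H1 already counts the 2-hour day-1 volume, and F2 already keeps participants on site until 2 hours after the infusion.
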